#### **5.4 Data Safety Monitoring Board (DSMB)**

Well qualified members were selected to serve on the Data Safety Monitoring Board (DSMB). The DSMB was established prior to study initiation to review data throughout the study, including review of 12-week data to enable the enrollment of adolescent subjects in TOL-3021 studies. The DSMB recommended that the protocol be amended to include subjects aged 12 - <18 years of age and this was submitted to FDA. If no objection is received from FDA, the protocol will include this subgroup and sites will be notified that they may begin enrollment of subjects aged 12 - <18. Once amended, data from adolescent participants will be summarized and presented separately from data on adult participants in all subsequent DSMB review meetings. The DSMB will also review data from an interim analysis when the first 30 subjects have completed 24 weeks of treatment.

The Sponsor and Emmes will support the DSMB in completing its charter and in all aspects of fulfilling its responsibilities. The DSMB will monitor the progress of the study, review safety data, and make recommendations regarding continuation, termination, or modification of the study. Specific items reviewed by the DSMB will include, but will not be limited to: study demographic information; interim/cumulative data for evidence of study-related AEs; protocol deviations; data quality, completeness, and timeliness of visits; factors that might affect the study outcome or compromise the confidentiality of the trial data (such as treatment and endpoint unblinding); and factors external to the study, such as scientific or therapeutic developments that may impact subject safety or the ethics of the study. The number of subjects who discontinue study treatment will also be included in the reports prepared for the DSMB. In addition to regular meetings, the DSMB chair may convene a full DSMB for review of an emergent issue.

DSMB recommendations will be carefully considered by the Sponsor. If a disagreement arises between the Sponsor and the DSMB, the Sponsor will discuss it with the DSMB in order to reach consensus. If attempts to reach a consensus fail, the Sponsor's opinion will prevail. In such situation, the Sponsor will inform the regulatory authorities, if needed.

## **5.5 Concomitant Medication**

### **5.5.1 Required Medications**

Subjects are required to use insulin regimens consistent with standards of care as advised by their primary physician or the PI.

### **5.5.2 Permitted Medications**

Concomitant medications required for standard care are permitted, except for those specified in Section 5.5.3 below as prohibited medications. Use of all concomitant medications must be documented in source documents and reviewed at each visit. Medications taken within the last three months before screening will be documented in an eCRF. Subjects will be encouraged to avoid making changes to their concomitant medication regimen during their participation in the study. Any change to a subject's concomitant medication regimen after randomization will be documented in an eCRF. In addition, PIs are encouraged to avoid adding to or changing a subject's medications during study participation unless deemed medically necessary. As clinically indicated, all standard vaccinations are permitted prior, during, and after the treatment period. Preferably, vaccinations should be given in between weekly TOL-3021 dosing and in a muscle that has not been used in the previous 2 weeks for TOL-3021 administration. Hormonal replacement therapy for emergent hypothyroidism or adrenal insufficiency can be started during the course of the study if recommended by the subject's primary endocrinologist.

### **5.5.3 Prohibited Medications**

Use of the following medications are prohibited from 30 days prior to randomization through the Week 52 final study visit:

- Systemic glucocorticoids or immunosuppressive agents (e.g., cyclosporine, azathioprine, methotrexate, infliximab, or biologic agents). A short course (<21 days) of systemic glucocorticoids for treatment of a transient condition (e.g., asthma) or replacement therapy for adrenal insufficiency is permitted.
- Medications other than insulin for glycemic control (e.g., metformin, sulfonylureas, glinides, thiazolidinediones, GLP1-RAs, DPP-IV inhibitors, pramlintide, or SGLT-2 inhibitors).
- Verapamil,  $\alpha$ -methyldopa.
- Investigational drugs or devices.
- Acetaminophen >4,000 mg per 24-hour period.

- Biotin

## 5.6 Diabetes Management

Glycemic control in all study subjects will conform with an accepted standard of “intensive” management. HbA1c will be assessed every 3 months (or as per schedule of events) to evaluate metabolic control. All individuals will be encouraged to strive for targets in accordance with current ADA recommendations: HbA1c of 7% for all adult subjects and modified for younger subjects to also have an HbA1c target of 7%, preprandial glucose levels of 90–130 mg/dL, postprandial levels of less than 180 mg/dL, and bedtime levels of 110-150 mg/dL. All subjects will generally receive three or more injections of insulin daily, including short- and long-acting insulin analog products. Alternatively, subjects may use continuous subcutaneous insulin infusion by insulin pump. Consistent with ADA Standard of Care Guidelines, glucose levels should be checked multiple times daily. All subjects should properly use their CGM device every day, which includes checking the meter results frequently. On the basis of glucose measurements, the Diabetes Management Team (DMT) may advise, as may be needed, the subject’s physician about possible adjustments in the insulin regimen, dietary modifications, including referral to a registered dietitian, or other approaches that the DMT believes could improve the glucose control. Subjects may be contacted by the diabetes educator or other professional at the site between visits to counsel subjects. Insulin use will be recorded daily using the CGM device and hypoglycemic events will be captured at each visit on the appropriate eCRFs. For purposes of achieving sustained good glycemic control subjects will be encouraged to record glucose, insulin dose, and dietary information, and to share this information at clinic visits. This information is for clinical care and is not to for database entry.

### The Diabetes Management Team

The Diabetes Management Team (DMT) is a resource for ensuring that all subjects maintain good glycemic control while avoiding hypoglycemia and acidosis. The DMT could include qualified members from Emmes, Sponsor, clinical sites, or a remote group assigned by the study Sponsor to review HbA1c, blood glucose data, and adverse events (AE) associated with diabetes self-management issues, such as hypoglycemia and DKA, and be of assistance on a PRN basis when requested by PI/Study Coordinator in order to prevent poor glycemic control in subjects enrolled in this study.

## 6 RANDOMIZATION

Subjects will be randomized in a 2:1 ratio of treatment with TOL-3021 to placebo. Randomization will be performed via a secure electronic data capture (EDC) system,

Advantage eClinical. Randomization will be stratified by duration of diabetes: 0-<1 year and 1-5 years, to ensure balance of TOL-3021 and placebo within each strata. The randomization code will be prepared by an unblinded statistician at Emmes and will be provided to the designated distributor that will package and ship study drug to the sites. Study drug will be labeled with the blinded numeric code provided by the statistician. Advantage eClinical will assign study drug vials to each study subject.

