## **3 TRIAL DESIGN**

The SUNRISE study is a prospective, multi-center, randomized, placebo-controlled trial in subjects aged 12.0 to <41.0 years diagnosed with T1D, as defined by ADA criteria, and within 5 years of diagnosis. Time of diagnosis is defined as the first day of insulin administration. The study is triple-blind through the analysis at Week 24, after which the Sponsor will be group unblinded. The study will continue through Week 52 as double-blind with site staff and subjects blinded. Subjects will be stratified by duration (zero up to 1 year and 1 year up to five years) to ensure balance of disease duration across treatment and placebo groups in each strata. For analytical purposes, all subjects 12-<41 will be considered cohort A, subjects aged 12-<18 will be considered cohort B and subjects aged 18-<41 will be considered cohort C. For subjects aged 12-<18 (Cohort B), dosing will be staggered with an initial 6 subjects aged 14-<18 being enrolled with the last subject having a minimum of 2 injections with at least 1 week follow-up after the 2nd injection. Safety data from this cohort will be evaluated before opening the study subjects 12 and older. Subjects should be randomized no sooner than 6 weeks after diagnosis, unless blood glucose is adequately controlled as indicated by time in range >55% with CGM. Screening assessments will include a physical examination, a fundus photography examination, chemistry and hematology safety labs, urinalysis, urinary protein screen (if positive a 24-hour collection for urine protein and creatinine will be obtained), HbA1c, presence of T1D antibodies, and a MMTT. Up to 99 qualified subjects who meet all selection criteria will be randomized in a 2:1 ratio to treatment with TOL-3021 or placebo and treated for 52 weeks (Figure 3). Subjects will agree to diabetes management during the

study with the goal of maintaining HbA1c levels of approximately 7.0% without frequent episodes of hypoglycemia.

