When the first 30 treated subjects completed the Week 12 visit, all available data was compiled and provided to the DSMB to consider if the enrollment of adolescent subjects in TOL-3021 studies can be recommended. Summary and individual subject data were provided for DSMB and FDA review. The DSMB confirmed that the protocol can be amended to include subjects aged 12 - < 18 years of age and submitted to FDA. If no objection is received from regulators and IRBs, sites will be notified that they may begin enrollment of subjects aged 12 - <18.

Subjects and investigators will be blinded to treatment assignment throughout the study. Selected Emmes staff will have access to treatment assignments. The primary data analysis will be conducted on data collected through Week 24. Cohorts B and C may be analyzed

separately. An interim analysis will be completed after the first 30 patients have completed 24 weeks. Results of the interim analysis will be shared with the DSMB and with a limited number of Tolerion staff, not directly involved in running the trial. Unblinded data summaries including safety outcomes and efficacy assessments will be prepared for the sponsor during the study using all data collected through Week 36. Final analysis of the data will be conducted at 52 weeks. The data summaries are unblinded to Sponsor and Emmes, the CRO, only.

Subjects will continue in the study for a 2-year safety follow-up period after completion of the 52-week double-blind study. During this 2-year follow-up subjects will have clinic visits at 18, 24, and 36 months from their first dose in the double-blind study to evaluate safety. At each of these follow-up visits a MMTT will be administered. Subjects may also be offered the opportunity to continue on study medication in a follow-on protocol for one or more years. Any follow-on study will continue to monitor subject safety in line with the requirements of the SUNRISE protocol.

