## 13 STATISTICAL CONSIDERATIONS

### 13.1 Sample Size/Power Considerations

Up to 99 subjects will be randomized 2:1 to active and placebo treatments. For analytic purposes all subjects 12- <41 years of age will be considered cohort A. A minimum of 18 and a maximum of 24 subjects aged 12 and <18 years of age will comprise Cohort B. Adult subjects aged 18- <41 will comprise cohort C. The proposed study is powered to detect approximately an overall 13% difference between treatment and placebo groups in a repeated measures mixed model analysis of the mean plasma C-peptide AUC over 4-hour MMTT at Week 12, 16, and 24 weeks as compared to the subject's baseline. A total of 90 subjects will provide 90% power to detect this difference at a significance level (alpha) of 0.05; a total of up to 99 subjects will be randomized to allow for an anticipated drop-out rate of approximately 10%. Insulin secretion as reflected by C-peptide declines more rapidly in younger patients, including adolescents. TOL-3021 is expected to have equal or even greater effect in the adolescent population compared to the effect observed in the phase 2a study of adult subjects only. An effect was detectable in the 17 adults who received 12 weeks of 1.0 mg treatment in that study. Based on assumption of an overall difference between treatment and placebo groups of 20%, then a minimum of 18 adolescents aged 12- <18 (Approximately 12 active and 6 placebo) would provide 80% power to detect a difference at a significance level (alpha) of 0.05, providing an initial estimate of efficacy and a description of safety in this population Cohort B (ages 12- <18) and cohort C (ages 18- <41) and will be analyzed separately as well as combined.

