#### **13.3.2 Safety Analysis**

All randomized subjects who received treatment will be included in a final safety data analysis which will include all data through Week 52 as the as-treated cohorts. In addition to descriptive summaries of all AEs by treatment group, Fisher's Exact test will be used to compare the incidence of the most frequent AEs or SAEs between treatment groups. The MedDRA system will be used to map each AE verbatim term to the system organ class (SOC) and preferred term (PT) for summary purposes. AE data, including the AE verbatim term and the associated AE preferred term, will be provided in the subject data listings. Note that once enrollment of TOL-3021 studies is expanded to adolescent participants aged 12.0 to <18 years of age, data from adolescent participants will be summarized and presented separately from data on adult participants in all subsequent DSMB review meetings.

Adverse event incidence summaries, including incidence rates of SAEs and TEAEs, will be generated on a monthly basis on live data. These will be reviewed in real time by the Sponsor and Emmes, with the treatment groups labeled as "A" and "B." An excessive rate in any specific AE or SAE may result in referral to the DSMB for review. The study statistician will maintain these reports and all resulting correspondence. The code may be requested to be broken by the DSMB after receiving Sponsor approval.

Other safety data, such as laboratory data, physical examination data, and abnormal findings, will be tabulated and/or graphically displayed. Concomitant medications used during the study will be summarized. Medications discontinued prior to the randomization date will be excluded from the summary.

Safety data collected after Week 52 will be analyzed separately from safety data collected during the controlled trial period.

After 6 subjects aged 14-<18 years of age have been enrolled with the last subject having a minimum of 2 injections with at least 1 week follow-up after the 2nd injection. Safety data from these initial subjects will be evaluated before opening the study to subjects 12 and older.

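### Stratifying by disease duration alone leaves to chance how many of the first six adolescents receive TOL-3021 and, secondarily, the roughly 12:6 split behind the Cohort B power

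*Protocol*

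**What the plan says.** The Synopsis (Study Procedures), Section 3 and Section 6 of the protocol agree on one stratification factor, disease duration in two strata. Section 3 puts it as "Subjects will be stratified by duration (zero up to 1 year and 1 year up to five years) to ensure balance", and Section 6 as "Randomization will be stratified by duration of diabetes: 0-<1 year and 1-5 years, to ensure balance of TOL-3021 and placebo within each strata". Allocation is 2:1. No section gives age as a factor, a separate adolescent list, or a set split for the first adolescents.

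Three other parts of the protocol use age-specific numbers:

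- **The first six adolescents.** In Section 3, "dosing will be staggered with an initial 6 subjects aged 14-<18 being enrolled". Section 13.3.2 adds: "Safety data from these initial subjects will be evaluated before opening the study to subjects 12 and older". The last of the six must have had two injections and at least a week of follow-up.
- **Cohort B power.** Section 13.1 states that "a minimum of 18 adolescents aged 12- <18 (Approximately 12 active and 6 placebo) would provide 80% power", for an assumed 20% difference at alpha 0.05, and that "Cohort B (ages 12- <18) and cohort C (ages 18- <41) and will be analyzed separately as well as combined". Cohort B is to number 18 to 24.
- **The primary model.** Section 13.3.3 adjusts for age group as well as baseline C-peptide AUC and duration group.

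Adolescent enrolment had not opened when this version was written. Section 3 says: "If no objection is received from regulators and IRBs, sites will be notified that they may begin enrollment".

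**The concern.** Stratification with blocking controls the arm split only within the strata it names. Adolescents share the duration strata with adults, so the 2:1 ratio holds among them in expectation but is not controlled.

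Two numbers matter. The first is how many of the six initial adolescents receive TOL-3021. Their safety review precedes dosing of children as young as 12, and adolescents on placebo tell it nothing about the drug. The second is the number of adolescents on placebo, which drives the precision of the separate Cohort B comparison. Having age group in the primary model adjusts the overall comparison but changes neither count.

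This is not detail that can wait for an analysis plan. The factors are fixed in the protocol, and an analysis plan cannot alter how subjects were allocated.

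**Working it through.** **Inputs.** From the protocol: 2:1 allocation; two duration strata; six initial adolescents; Cohort B minimum 18 at about 12:6, 20% difference, 80% power, alpha 0.05 (taken as two-sided, following Section 13.3.3); overall trial 90 evaluable (60:30 at 2:1), 13% difference, 90% power. Not stated, so assumed and varied: block size (3, 6 or 9), share with new-onset disease (10–50%), when adolescents start to enter, and whether they enter mixed with adults or consecutively.

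**1. Initial six.** Under independent 2:1 assignment the number active is Binomial(6, 2/3).

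- P(2 or fewer) = (1 + 12 + 60)/729 = 73/729 = 0.100
- P(3 or fewer) = (73 + 160)/729 = 233/729 = 0.320

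Simulated permuted blocks within the duration strata tighten this:

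| Assignment and entry | 2 or fewer active | 3 or fewer active |
|---|---|---|
| Independent 2:1 | 10% | 32% |
| Blocks, mixed with adults | 4–8% | 28–31% |
| Blocks, consecutive adolescents | 1–7% | 19–31% |

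**2. Placebo count among 18 adolescents.**

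| Assignment and entry | 4 or fewer placebo | 3 or fewer placebo |
|---|---|---|
| Independent, Binomial(18, 1/3) | 23% | 10% |
| Blocks, mixed with adults | 13–21% | 3–8% |
| Blocks, consecutive adolescents | 1–10% | 0–2% |

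The lower ends of the mixed row arise when adolescents make up a larger share of the remaining enrolment. At the permitted 24, independent assignment gives 6% and 2%.

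**3. The stated 80%.** No SD is given, so the figure can only be calibrated. With the normal approximation, SD = difference / [(z₀.₉₇₅ + z_power) × √(1/n₁ + 1/n₂)]:

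- Cohort B: 0.20 / [(1.960 + 0.842) × √(1/12 + 1/6)] = 0.20 / (2.802 × 0.5) = 0.143
- Overall trial: 0.13 / [(1.960 + 1.282) × √(1/60 + 1/30)] = 0.13 / (3.242 × 0.2236) = 0.179

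The two statements imply different SDs. With 0.179 at an exact 12:6, power = Φ(0.20/(0.179 × 0.5) − 1.960) = Φ(0.27) ≈ 61%. Using the t distribution it is 55–56%. Normal calculations on raw and log scales give 58–64%.

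**4. Power by split, taking 80% at 12:6 as given.** Standardised effect 1.492 (noncentral t), noncentrality 1.492 × √(n₁n₂/18):

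| Active:placebo | 10:8 | 11:7 | 12:6 | 13:5 | 14:4 | 15:3 |
|---|---|---|---|---|---|---|
| Power | 84% | 83% | 80% | 76% | 70% | 60% |

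Averaged over chance splits, power is 77% (independent) to 80% (blocked, consecutive), a loss of at most about 3 points.

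**5. After the change.**

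- Single adolescent list, blocks of 3 or 6: exactly 12:6, and 4 active among the first six, in every run.
- Age by duration strata, blocks of 3: 5–7 on placebo, and 3–5 active among the first six (exactly 3 in 14–16% of runs).
- Age by duration strata, blocks of 6: 4–8 on placebo, and 2 or fewer active among the first six in about 2%.

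**The case against.** Much of the case on the other side stands, and it limits the weight of the point.

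- **A reader might infer that the protocol contradicts itself.** It does not. The 12:6 is given as approximate and is what 2:1 allocation yields on average. Section 13.1 presents Cohort B as a first efficacy estimate plus a safety description, and the Synopsis and Section 3 say only that the cohorts may be analysed separately.
- **A reader might infer that Cohort B stands to lose much power.** Only an unlucky split does that. Splits with more placebo gain slightly, and the average loss is small.
- **A reader might infer that the review of the six is the only protection for younger adolescents.** It is not. The DSMB and FDA received the Week 12 data on the first 30 subjects beforehand (Section 3). The six have an on-site Week 3 injection visit, stopping rules apply (Section 5.3.2), event summaries are run monthly (Section 13.3.2), and adolescent data go separately to later DSMB meetings (Section 5.4). Nothing shown prevents the unblinded statistician from telling the reviewing body how many of the six were active.
- **Six subjects are a coarse screen at any split.** With no events, the one-sided 95% upper bound on an event rate is 1 − 0.05^(1/n): 78% with 2 active, 63% with 3, 53% with 4, 45% with 5. Three active is a modest loss against four, and age by duration strata can still produce three. Two or fewer is the clearly worse outcome.

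None of this shows that age is controlled anywhere. The other safeguards reduce the consequence of a poor split but do not prevent one.

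**Conclusion.** The point holds as a modest, inexpensive design improvement. The protocol attaches a review step and a stated power to adolescent-specific numbers while randomising on duration alone. The initial six come first: 2 or fewer on TOL-3021 in about 1–10% of realisations, and 3 or fewer in about 19–32%. The Cohort B split is secondary: 4 or fewer on placebo in about 13–23% and 3 or fewer in about 3–10% if adolescents are mixed with adults or assigned independently, and less often if they enrol consecutively.

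The ranges rest on assumed block sizes and entry patterns, and the power figures on accepting 80% at 12:6. The documents do not support reading this as a threat to the primary analysis, which covers all ages and adjusts for age group. Nor do they support the hope that stratifying would deliver the stated 80%. That figure has no SD behind it, and the gap to 55–64% is far larger than anything the split causes.

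**What to change.** Before the first adolescent is randomised, add age group (12 to under 18, 18 to under 41) as a stratification factor with 2:1 blocks, and conceal the block size from sites and sponsor. Either form works:

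- **Single adolescent list, blocks of 3 or 6.** This fixes 12:6 at 18 subjects and 4:2 among the first six. It gives up duration balance among adolescents, although duration group remains in the primary model. Blocks of 6 reach the same split and are less predictable than blocks of 3.
- **Age by duration strata, blocks of 3.** This keeps duration balance and bounds both splits without fixing them.

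The cost is a revised adolescent list in the electronic data capture system, issued when their enrolment opens. Existing assignments do not change and no patients are added. Expect one or two more incomplete blocks. Small blocks also make assignments somewhat more predictable, which matters because the sponsor and CRO see monthly event summaries by coded arm (Section 13.3.2).

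Separately, Section 13.1 should state the SD behind the Cohort B power, or describe that comparison as estimation without a power claim.
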